7.2 Method of Treatment Assignment

All participants will be randomized using an Interactive Response Technology (IRT). Before the study is initiated, each user will receive log in information and directions on how to access the IRT.

Study treatment will be dispensed at the study visits as listed in Schedule of Activities ([Section 2](#)).

Participants will be randomized to receive either abatacept or placebo according to a computer-generated randomization scheme prepared by a Randomization Coordinator within the Drug Supply Management Department of BMS Research and Development.

Enrolled participants, including those not dosed, will be assigned sequential participant numbers starting with 00001, (eg, 00001, 00002, 00003.... 00010).

During the screening visit, the investigative site will call into the enrollment option of the Interactive Response Technology (IRT) designated by BMS for assignment of a 5-digit participant number that will be unique across the study. Enrolled participants, including those not dosed, will be assigned sequential participant numbers starting with 00001, (eg, 00001, 00002, 00003....

00010). The patient identification number (PID) will ultimately be comprised of the site number and participant number. For example, the first participant screened (ie, enrolled) at site number 1, will have a PID of 0001 00001. Once it is determined that the participant meets the eligibility criteria following the screening visit, the investigative site will call the IRT to randomize the participant into the double-blind panel. Participants meeting all eligibility criteria will be randomized in a 2:1 ratio to treatment arms. The randomization schedule will be generated using permuted blocks of fixed size within each stratum, defined by age group and remdesivir use. Once enrolled in IRT, enrolled participants will be randomized through the IRT prior to the start of study treatment. At randomization the participants will be stratified according to age group at randomization (< 60 vs ≥60) and by remdesivir Use (Yes [RemYes] vs No [RemNo]). Remdesivir Use = Yes, will be defined as a subject having been dosed with remdesivir or for whom the decision to dose with remdesivir based on availability is Yes. Remdesivir Use = No will be defined as subjects that will not utilize or have not utilized remdesivir. The exact procedures for using the IRT will be detailed in the IRT manual.

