9.1.1.2 Improvement in Clinical Status

The WHO has recommended clinical study for COVID-19 use a composite clinical endpoint and recommend use of an ordinal scale that measures participant's clinical status.⁴⁸ Ordinal data is a kind of categorical data with a set order or scale to it. Ordinal scales have been adopted in some current prospective clinical studies.⁴⁹ The following 8-point scale was proposed for the National Institute of Allergy and Infectious Diseases (NIAID) Adaptive COVID-19 Treatment Trial (ACTT) (ClinicalTrials.gov Identifier: NCT04280705). It will be used in this study.

- 1) Death
- 2) Hospitalized, on invasive mechanical ventilation or extracorporeal membrane oxygenation (ECMO)
- 3) Hospitalized, on non-invasive mechanical ventilation or high-flow oxygen devices
- 4) Hospitalized, requiring supplemental oxygen
- 5) Hospitalized, not requiring supplemental oxygen - requiring ongoing medical care (COVID-19 related or otherwise)
- 6) Hospitalized, not requiring supplemental oxygen - no longer requires ongoing medical care
- 7) Not hospitalized, limitation on activities and/or requiring home oxygen
- 8) Not hospitalized, no limitation on activities

Patients may change between states in this scale multiple times during any 24-hour period. The study team will record in the study record only the worst (ie, lowest) state for each day (midnight to midnight). The determination of the worst state to be recorded should be made as soon as possible after the completion of the day to be assessed.

ICU admission is defined as transfer of care within the hospital to a specialized medical care unit distinct from routine or intermediate (ie, stepdown) care. Given the increased demand for ICU beds as a consequence of the COVID-19 pandemic, all forms of ICUs (eg, surgical) and non-ICU beds have been converted into ICU care beds. Progression into any of these will be considered to meet these criteria.

Other elements of each point have been defined with the exception of ECMO (extra-corporeal membrane oxygenation). This scale captures similar information to the primary endpoint but has the advantage of capturing improvement. The “limitations of activities” in state #6 includes need for home oxygen therapy. Based on inclusion criteria, all study subjects will be in category 3 or 4, and can be extracted from the clinical record.

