10.3.1 Efficacy Analyses

Statistical analysis methods for efficacy analyses are provided in Table 10.3.1-1. The primary efficacy endpoint will be formally tested for difference between the treatment groups. Nominal p-values for treatment comparison will be provided for selected secondary endpoints.

Table 10.3.1-1: Efficacy Statistical Analyses

Endpoint	Statistical Analysis Methods
Primary Efficacy Endpoint	The comparison between treatment groups of the proportion of participants with primary endpoint event (mechanical ventilation or death) prior to or on Day 28 will be performed using the Cochran-Mantel-Haenszel (CMH) Chi-Square test, stratified by the randomization stratification factors age group (< 60, ≥ 60) and remdesivir use as well as baseline severity. Baseline severity will be defined by the Clinical Status scale at randomization. A one-sided significance level of 0.15 will be used to assess statistical superiority of abatacept over placebo. The ITT population will be used. Randomized

Table 10.3.1-1: Efficacy Statistical Analyses

[figure not shown]
Endpoint	Statistical Analysis Methods

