	
participants with no primary endpoint assessment due to withdrawal of consent or for other reasons will be imputed as treatment failures (ie. progressors). The OR along with its 2-sided 70% CI and 95% CI, as well as the absolute treatment difference in proportions with its 95% will be presented. The construction of CIs for absolute differences in proportions between treatment groups will be based on minimum risk weights⁵⁹ to account for randomization stratification factors and baseline severity.
 
A supplemental analysis of the primary endpoint comparison between the treatment groups will be based on logistic regression with age as a continuous covariate and factors for baseline severity and remdesivir stratification in the model. The nominal p-value for the Chi-square test based on this model will be presented.
 
The primary endpoint is a composite endpoint. The number and percentage of participants progressing to each of the components will be presented by treatment group.
 
The proportion and 95% CI of participants with mechanical ventilation or who died prior to or on Day 28 within treatment group as well as the difference in proportions between the treatment groups and its 95% CI will also be presented by site, age-subgroup (< 60, ≥ 60), remdesivir use (stratification factor), gender, and baseline severity.
 
Kaplan-Meier estimates for the time from randomization to progression to the primary endpoint will be presented. The p-value for the treatment comparison based on the stratified log-rank test, stratified by age-group and remdesivir use, will be presented as a sensitivity analysis of the primary endpoint.

Secondary Binary Endpoints:
	
Proportions and 95% CIs for the binary efficacy endpoints will be presented by treatment group. CIs for proportions within treatment groups will be based on normal approximation. Difference in proportions and 95% CI will be presented, as well as the nominal p-value derived from the CMH Chi-square test stratified by baseline severity and the randomization stratification factors. The construction of CIs for differences in proportions between treatment groups will be based on minimum risk weights to account for randomization stratification factors and baseline severity. A missing response value due to withdrawal of consent or for other reasons will be imputed as a non-responder or progressing.

Table 10.3.1-1: Efficacy Statistical Analyses

Endpoint	Statistical Analysis Methods

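### The log-rank sensitivity analysis of the primary endpoint leaves out baseline severity, which the primary test and every other efficacy test adjust for

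*Protocol*

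**What the plan says.** All of this is in the Protocol, and most of it in section 10.3.1, Table 10.3.1-1.

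- **Primary test:** a CMH test, "stratified by the randomization stratification factors age group (< 60, ≥ 60) and remdesivir use as well as baseline severity".
- **Severity:** "Baseline severity will be defined by the Clinical Status scale at randomization". I read this as the 8-point ordinal scale of section 9.1.1.2, which adds: "Based on inclusion criteria, all study subjects will be in category 3 or 4". Severity therefore has two levels.
- **Supplemental model for the primary endpoint:** "logistic regression with age as a continuous covariate and factors for baseline severity and remdesivir stratification in the model".
- **Secondary binary endpoints:** a "CMH Chi-square test stratified by baseline severity and the randomization stratification factors".
- **Ordinal secondary endpoint:** a row-mean-scores CMH test stratified by age group, remdesivir use and baseline severity.
- **Confidence intervals for differences in proportions:** the minimum risk weights also account for baseline severity.
- **Time to the primary endpoint:** Kaplan-Meier estimates and a "stratified log-rank test, stratified by age-group and remdesivir use, will be presented as a sensitivity analysis of the primary endpoint".
- **Randomization (section 7.2):** "permuted blocks of fixed size within each stratum, defined by age group and remdesivir use".

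The log-rank test is the only between-group test in the table that omits severity. No reason is given. The protocol names the strata itself, so this is not a detail left open for the SAP.

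**The concern.** Of the three factors in the primary test, randomization stratifies on two. The log-rank test keeps those two and drops the third, the only one whose balance is left to chance.

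The protocol's own definitions suggest that this factor could matter. Category 3 is non-invasive ventilation or high-flow oxygen, and section 9.1.1.4 counts both as respiratory failure. Baseline severity therefore separates participants already in respiratory failure from the rest, in a trial whose endpoint is invasive ventilation or death.

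The log-rank result will be read beside the CMH result as a check on it. If the arms differ in severity by chance, the CMH test adjusts for the gap and the log-rank test does not. The two could then disagree for a reason unrelated to the time-to-event approach.

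**Working it through.** **1. The plan's own figure.** Inputs from section 10.1: 25% against 10%, one-sided 0.15, 80% power, 2:1, continuity-corrected chi-square.
- Pooled rate = (0.25 + 2 × 0.10)/3 = 0.15.
- Uncorrected placebo n = [1.036 × √(3 × 0.15 × 0.85) + 0.842 × √(2 × 0.25 × 0.75 + 0.10 × 0.90)]² / (2 × 0.15²) ≈ 32.8.
- Corrected n = (32.8/4) × [1 + √(1 + 6/(32.8 × 2 × 0.15))]² ≈ 42.2, so 43 placebo and 86 abatacept.

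The stated 129 is reproduced. It does not depend on the log-rank strata.

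**2. Strata side by side.**

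| Procedure | Age | Remdesivir | Severity |
|---|---|---|---|
| Randomization | yes | yes | no |
| Primary CMH | yes | yes | yes |
| Supplemental logistic model | yes (continuous) | yes | yes |
| Secondary CMH | yes | yes | yes |
| Ordinal row mean scores | yes | yes | yes |
| Log-rank | yes | yes | **no** |

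The CMH test has 2 × 2 × 2 = 8 cells and the log-rank test has 4.

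**3. Size of a chance gap.** The documents do not give the category 3 share, so I assume 20-30%. The SD of the difference in share between arms is √(q(1 − q)(1/86 + 1/43)).
- q = 0.30: √(0.21 × 0.0349) = 0.086, or 8.6 points.
- q = 0.20: √(0.16 × 0.0349) = 0.075, or 7.5 points.

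Assume also event rates of 50% in category 3 and 14% in category 4. These average 0.3 × 0.50 + 0.7 × 0.14 = 0.248, close to the design's 25%. With no treatment effect, a one-SD gap then shifts the expected event-rate difference by 0.086 × 0.36 = 0.031. That is about 3 points, against a design difference of 15.

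**4. Effect on the p-value.** I simulated 1,000 trials per scenario: N = 129, 2:1 in blocks of six within age group by remdesivir use, 20-30% in category 3, and an event odds ratio of 4-8 for category 3 against 4. The overall event rate was 25% with no effect, and the treatment odds ratio was 1/3 under the alternative. The protocol sets no threshold for the log-rank p-value, so the primary test's one-sided 0.15 serves as the yardstick.

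| | Log-rank as written | Log-rank with severity |
|---|---|---|
| No effect, all randomizations | 15-16% | 15-16% |
| No effect, abatacept about 10 points fewer in category 3 | 23-29% | 14-16% |
| No effect, abatacept about 10 points more in category 3 | 4-8% | 15-16% |
| Power, treatment odds ratio 1/3 | 81-85% | 82-86% |
| Different verdict from the primary CMH, all randomizations | 4-10% | 2-6% |

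A gap of 10 points or more arose in about 17-27% of trials. The Monte Carlo standard error near 15% is √(0.15 × 0.85/1000) ≈ 1.1 points.

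A separate run used 30% in category 3 and event rates of 50% and 14%. With no effect and a gap above 7 points, the test as written rejected in 30% or 5% of trials by direction, against 16-17% with severity added.

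**5. Cost in power.** This used 3,000 trials per scenario, marginal rates of 25% and 10%, and event times uniform over Days 1-14. Going from 4 to 8 strata moved log-rank power from 85.9% to 86.7% when severity was prognostic, and from 86.5% to 85.3% when it was not. Each estimate has a standard error of about 0.6 points.

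**The case against.** **The choice is conventional.** Stratifying a log-rank test by the randomization factors is common practice, and the protocol nowhere says that all analyses must share one adjustment set. This stands: the text does not contradict itself, and the test as written is not invalid.

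**Severity is randomized too.** It is balanced in expectation, and over all randomizations the log-rank test holds its level at 15-16%. A reader might infer that omitting severity biases the test or inflates its error rate. The documents and the simulation do not support that. What remains is the effect of a chance gap in the one trial that is run.

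**Little hangs on this p-value.** Section 10.3.1 formally tests only the primary endpoint, and no decision rule uses the log-rank result. The primary test, the confidence intervals and the logistic model all adjust for severity. Results are also shown by severity, and the baseline scale is tabulated by arm, so an imbalance would be visible. This stands and keeps the point minor.

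**Sparse cells.** The design implies 86 × 0.10 + 43 × 0.25 ≈ 19 events, or about 2.4 per cell over eight cells. This does not justify the omission, because the primary CMH test already uses the same eight cells and the measured loss is about 1 point of power.

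**A sensitivity analysis may vary the adjustment.** It may. It is also tempting to say that matching the strata would let any disagreement be put down to event timing or censoring. That goes too far. The CMH test counts unassessed participants as progressors, and the protocol does not say how the log-rank test treats them. Even with severity added, the two tests differ in 2-6% of simulated trials.

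**Conclusion.** The point holds as a minor inconsistency that is cheap to remove. The log-rank test is the one between-group efficacy test in Table 10.3.1-1 that omits baseline severity, and severity is the one primary-test factor not protected by stratified randomization.

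The test is sound on average. Its weakness is conditional: at a 10-point chance gap its one-sided 0.15 behaves like 23-29% or 4-8%, and such gaps or larger arise in about 17-27% of trials. Over all randomizations, adding severity lowers disagreement with the primary test from about 4-10% to 2-6%.

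These sizes rest on assumptions that the documents do not supply: 20-30% of participants in category 3, and an event odds ratio of 4-8 for that category. If severity is weakly prognostic, or nearly everyone starts in one category, the effect shrinks towards nothing. The primary test, its significance level and the sample size of 129 are unaffected.

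**What to change.** In Table 10.3.1-1, stratify the log-rank test by age group, remdesivir use and baseline severity, the same strata as the primary CMH test. If the sponsor prefers to keep four strata, one sentence giving the reason would do.

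The cost is one phrase. Baseline severity is already needed for the primary test, so no data collection, sample size or trial procedure changes. The downside is about 1 point of log-rank power if severity turns out not to be prognostic.

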Due to the novel design of this study and limitations imposed by the risk of contagion, the study will be monitored by a Safety Oversight Committee (SOC). The SOC will assist in the oversight of the study execution and ongoing assessment of safety and efficacy. Members will be chosen based on clinical expertise in the areas of infectious disease, pulmonary/critical care and

immunotherapy (eg rheumatology) or study outcome interpretation. The SOC will be composed of BMS personnel, site investigators and external experts. External members will constitute the majority of all voting members. The SOC will be provided with periodic data outputs and meet on a regular schedule (ie bi-weekly) or ad hoc basis as needed. The first meeting of the SOC will review the SOC charter and decide on the frequency of SOC data review meetings before finalizing the SOC. In the case that review of subjects grouped by treatment is required to assess changes to study conduct, this will be performed by a group of external members in a closed session. Details of the membership, meeting schedule, purpose and data access is found in the SOC charter.

Statistical considerations

A 25% estimated rate of progression under placebo plus standard of care to one of the elements of the primary endpoint is derived from available literature. A two group continuity corrected χ^2 test with a 0.150 one-sided significance level will have 80% power to detect the difference between a proportion of 10% abatacept treated participants and a proportion of 25% participants in the placebo group with a primary endpoint event (odds ratio of 0.33, ie odds of progression under abatacept versus placebo) when the sample sizes are 86 and 43, respectively (a total sample size of 129). This computation was made using nQuery Advisor version 7. The target sample size for this study is approximately 129 randomized participants.

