4 OBJECTIVES AND ENDPOINTS

Table 4-1: Objectives and Endpoints

Objective	Endpoint
Primary	

 Prevention of Disease Progression 	
 Proportion of participants with composite end point of mechanical ventilation or death prior to or on Day 28
Secondary	

 Improvement in clinical status 	
 Change from baseline in the Ordinal 8-point Outcome Scale on Day 28

 Improvement in mortality 	
 All-cause mortality on Day 28

 Absence of critical disease 	
 Proportion of participants alive and free of respiratory failure on Day 28

 Recovery of pulmonary function 	
 Proportion of participants returned to room air by Day 28

 Shortened hospitalization 	
 Proportion of participants alive and discharged home by Day 28

 Safety 	
 Proportion of participants with SAEs and serious infections

Table 4-1: Objectives and Endpoints

Abbreviations:

SAE = serious adverse event;

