The study will include 129 randomized participants in a 2:1 ratio, abatacept: placebo, both on standard of care.

The study design schematic is presented in Figure 5.1-1.

Figure 5.1-1: Study Design Schematic

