9.1.1.3 Improvement in Mortality

Mortality for this endpoint will be based on all-cause mortality at Day 28 which represent participants who are in state 1 of the Ordinal 8-point Outcome Scale.

For participants deaths, data will be collected on whether the death occurred after withdrawal of care and, if so, the reason for withdrawal of care will be recorded (eg, brain death, patient/family request, resource constraint).

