10 STATISTICAL CONSIDERATIONS

10.1 Sample Size Determination

A 25% estimated rate of progression under placebo plus standard of care to one of the elements of the primary endpoint (mechanical ventilation or death) of hospitalized COVID-19 untreated patients (in particular patients without targeted therapy) was derived from available literature^{1,2,55,56,57,58} and anecdotal feedback. Rates of progression in these reports ranged from 8% to 32%. All reports are from China and include hospitalized patients that had respiratory symptoms. There are different definitions of progression in these reports but most are based on ICU and/or death.

A two group continuity corrected χ^2 test with a 0.150 one-sided significance level will have 80% power to detect the difference between a proportion of 10% abatacept treated participants and a proportion of 25% participants in the placebo group with a primary endpoint event (odds ratio of .33, ie, odds of progression under abatacept versus placebo) when the sample sizes are 86 and 43, respectively (a total sample size of 129). This computation was made using nQuery Advisor version 7. The target sample size for this study is approximately 129 randomized participants.

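### Normal-approximation 95% CIs are fixed for within-arm secondary proportions; for Day 28 mortality in arms of 43 and 86 they under-cover, and with no deaths they collapse to [0, 0]

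*Protocol*

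**What the plan says.** Protocol Section 10.3.1, Table 10.3.1-1, row for secondary binary endpoints: "Proportions and 95% CIs for the binary efficacy endpoints will be presented by treatment group", and "CIs for proportions within treatment groups will be based on normal approximation". The row offers no alternative for small counts and does not defer the choice to the SAP. The ordinal-scale row of the same table, by contrast, does leave further analyses to the SAP.

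Mortality falls under this row. Section 4 lists "All-cause mortality on Day 28" as a secondary endpoint, and Section 9.1.1.3 states: "Mortality for this endpoint will be based on all-cause mortality at Day 28".

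Section 10.1 gives the arm sizes, "when the sample sizes are 86 and 43, respectively (a total sample size of 129"), and the design rates: "a proportion of 10% abatacept treated participants and a proportion of 25% participants in the placebo group with a primary endpoint event". Section 10.2 uses all randomized participants for efficacy, so the planned denominators are 86 and 43.

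**The concern.** Read in its usual sense, a normal-approximation interval for a single proportion is the Wald interval, centred on the observed rate with its standard error estimated from that same rate. It works acceptably for mid-range proportions. It fails when events are few: the estimated standard error is too small when the observed rate happens to be low, the lower limit can be negative, and the width is zero when there are no events.

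Mortality is the secondary endpoint most exposed to this. The trial is meant for signal detection (Section 5.1), and these will be the error bars shown for the death rate in each arm. If the interval too often lies wholly below the true rate, a reader is told that mortality is better bounded from above than it is.

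**Working it through.** **Inputs.** Arm sizes 86 and 43, and composite rates 10% and 25% (Section 10.1); two-sided 95% level and normal approximation (Table 10.3.1-1). Mortality rates are assumptions, because the protocol states none.

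**The plan's own figure first.** With one-sided alpha 0.15 (z = 1.036), power 80% (z = 0.842), 2:1 allocation and pooled rate (0.25 + 2 × 0.10)/3 = 0.15, the standard formula gives 32.8 placebo participants without continuity correction and 42.2 with it. Rounded up, that is 43 and 86, total 129. The sample size reproduces and is not affected by this point.

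**Ceiling on mortality.** Section 9.1.1.1 defines the composite as invasive ventilation or death, so deaths cannot exceed composite events. Under the design rates the expected deaths are at most 86 × 0.10 = 8.6 and 43 × 0.25 = 10.75, and fewer if any ventilated participant survives.

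**Coverage.** With x deaths among n and q = x/n, the Wald interval is q ± 1.96 × sqrt(q(1 − q)/n). Exact coverage at true rate p is the sum of the Binomial(n, p) probabilities over every x whose interval contains p.

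One case in full, n = 43 and p = 5%: the intervals for x = 1 to 6 contain 5%. Zero deaths has probability 0.95^43 = 0.110 and gives [0, 0], below the truth. Seven or more deaths has probability 0.005 and gives an interval above it. Coverage is 1 − 0.110 − 0.005 = 0.885.

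| Assumed mortality | Wald coverage, n=43 | Interval wholly below truth, n=43 (nominal 2.5%) | Negative lower limit, n=43 | No deaths, n=43 | Wald coverage, n=86 |
|---|---|---|---|---|---|
| 3% | 72.8% | 27.0% | 69% | 27% | 92.3% |
| 5% | 88.5% | 11.0% | 72% | 11% | 92.9% |
| 8% | 86.2% | 13.1% | 52% | 2.8% | 91.2% |
| 10% | 92.9% | 6.2% | 35% | 1.1% | 92.9% |
| 12% | 89.2% | 9.7% | 22% | 0.4% | 94.2% |
| 15% | 89.5% | 9.6% | 10% | 0.1% | 94.1% |
| 25% | 92.7% | 6.1% | 0.2% | 0.0% | 94.9% |

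In every row at n = 43, misses above the truth are no more than 1.1%.

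**Averages.** Coverage oscillates with p, so it was also averaged on a fine grid (step 0.05 percentage points).

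- Over 3-15%: Wald 88.9% (n=43) and 91.8% (n=86); Wilson 95.6% and 95.3%.
- Grid minimum over 3-15%: Wald 72.8% and 79.8%; Wilson 92.9% for both.
- Over 40-70%: Wald 93.9% and 94.4%, so little is lost for mid-range endpoints.

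Clopper-Pearson at n = 43 covers 96.5-99.1% at the listed 3-15% rates, so it is conservative.

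**What would be printed.**

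- 2/43 deaths: q = 4.65%, standard error 3.21%. Wald −1.6% to 10.9%; Wilson 1.3% to 15.5%.
- 0/43 deaths: Wald 0 to 0; Wilson 0 to 8.2%.
- 0/86 deaths: Wald 0 to 0; Wilson 0 to 4.3%.

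**The case against.** The strongest reply is about weight. Section 10.3.1 formally tests only the primary endpoint. For mortality the treatment comparison rests on a nominal stratified CMH p-value and a difference interval built on minimum risk weights, and neither uses the within-arm interval. That is correct and caps the importance of the point.

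Second, the most striking figures come from assumed mortality of 3-5% in the placebo arm. At the rates tied to the protocol the shortfall is about two percentage points, and negative limits are rare (2.3% of trials at 10% with n=86, 0.2% at 25% with n=43). This also stands. But a shortfall remains when the averaging range is matched to the design ceilings: the mean is 90.6% over 3-25% at n=43 and 90.8% over 3-10% at n=86. The conclusion does not depend on a favourable choice of rate.

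Third, the 10% ceiling holds only if abatacept works as planned. If its composite rate were 25%, mortality could approach that figure, where coverage at n=86 is 94.9% and the problem nearly vanishes. That is fair for the abatacept arm; the placebo arm is unaffected by it.

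Fourth, [0, 0] is an uncommon result: 1.1% of trials at 10% mortality with n=43, and 1.2% at 5% with n=86. If the rule imputing missing values as progressing is applied to mortality as death, it is rarer still. True, but under-coverage occurs without it.

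Last, the Wilson interval is also derived from a normal approximation. The text does not name it, however, and the unqualified phrase ordinarily means Wald. A continuity correction would not rescue that reading at low rates: at 2% and n=43, coverage is 58.0% with it and 57.9% without.

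**Conclusion.** The concern holds. The protocol fixes an interval method that covers less than its stated 95% over almost all of the mortality range its own design rates allow: below 95% on 97% of a 1-25% grid at n=43, and on all of a 1-10% grid at n=86. The shortfall runs from about two points at the design ceilings to six points on average over 3-15% in the placebo arm, and more at the lowest rates. Its direction is consistent: the interval understates how high mortality could be.

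This rests on reading normal approximation as Wald, on the planned arm sizes, and on assumed mortality rates; only the 10% and 25% ceilings come from the protocol. The effect is confined to descriptive within-arm intervals. The sample size, primary test, nominal p-values and difference intervals are untouched. It should be corrected because the error is clear and the correction is easy, not because a trial decision turns on it.

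**What to change.** In the secondary binary endpoints row of Table 10.3.1-1, replace the normal approximation for within-arm proportions with Wilson score 95% intervals, or Clopper-Pearson if guaranteed coverage is preferred. Using one method for the whole row is simplest. It does no harm to mid-range endpoints, and it also helps any endpoint whose proportion is near 100%, because Wald coverage at p and at 1 − p is the same.

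The cost is a few words and a standard software option. The intervals become asymmetric, and Clopper-Pearson intervals are somewhat wider. No change is needed to the difference intervals, the subgroup displays, the primary test or the sample size.
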